Phase Three: Following recruitment, a research associate not otherwise involved in the study will screen participants prior to enrollment. Veterans will be randomized in a 1:1 ratio, with a research staff member utilizing and keeping the schedule. Veterans randomized to VACT-CP (and online website that includes 7 online-module based weekly sessions of treatment) via personal computer or provided laptop at the Bedford VAMC. Veterans in the waitlist control will be provided with a list of common pain resources at the Bedford VAMC. The VACT-CP program will be housed on a secure web server through Northeastern University, with no Veteran private health information collected by the system. Veterans in both conditions will complete the assessment battery (see Table 2 for specific schedule) at baseline, either in-person or remotely (via a phone call or online using the VA-approved Qualtrics survey platform) depending on the participant’s preference. In addition, the full battery of primary outcomes and process measures will be taken at mid-point of the intervention phase (3 weeks) and at the end, immediately following the treatment (7 weeks). Veterans will be tracked in terms of their post-referral treatment engagement (e.g., enrolling in any of the pain-resource options on the handout). In addition, a research associate will call the Veteran at weeks 3 and 6 and conduct a brief safety assessment with Veterans assess for potential suicidality, usability issues, and participant health and well-being.

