Demographics, functional health, and pain measures. Demographic measures will include pain-related information regarding type and duration, age, gender, race and ethnicity, and education. Well-being measures will include psychological depression, Patient Health Questionnaire-9 (PHQ-9), and PTSD Check List (PCL-5), as well as pain interference (Brief Pain Inventory), and the Veteran's RAND 36 Item Health Survey (VR-36). These measures will be used to describe the sample and will take approximately 30 minutes).

Media and Technology Usage and Attitudes Scale (Rosen et al., 2013): A 16-item measure of different attitudes toward technology using a 10-point frequency scale from Never (0) to All the Time (10) that assess comfort level, attitudes towards new technology, and usage patterns for mobile technology. Completed before usability/platform interaction session.

Post-Website Usability Interaction Measures

Intrinsic Motivation and Perceived Usefulness Scale (ITAM; Venkatesh, 2000): The usability survey items were adapted from an existing set of usability questions to make the questions specific to the VACT-CP online treatment. The items form 2-4 item subscales that will be used to address relationships between elements of our modified Integrated Technology Acceptance Model. We will assess antecedent conditions that are proposed to influence health-technology acceptance and use, including satisfaction with medical care, preferences for seeking information, health care needs, internet dependence, and health care knowledge. In addition, we will assess intrinsic motivation, perceived ease of use, and perceived usefulness of each health-technology. Prior versions of the subscales have shown good internal consistency reliability for each subscale (Cronbach's alphas > 0.7 for all but information seeking preference which was 0.60).

System Usability Scale (SUS; Brooke, 1996): a 10-item measure, scored on a 5-point Likert scale, that assesses human-computer interaction. A SUS score above 58 is regarded as above average, and a SUS score above 80 is regarded as high and a score above which participants are likely to recommend the product to friends. The SUS generates a subjective evaluation score using a globally accepted scale and to understand if the system in its current form is sufficiently usable.

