(SCID-5) to assess for potential psychosis, substance use disorders, or clinically-significant suicidality. Eligible subjects will then complete self-report measures. Participants with additional, co-morbid pain diagnoses will not be excluded. Data will be collected at baseline, the study midpoint (approximately 3 weeks), end of treatment/7 weeks, and at the one-month follow-up period. Self-report baseline and post-baseline assessments will be administered either in-person or online by Qualtrics, a VA-approved platform and vendor. Length of time for assessments will take approximately 2 hours for baseline assessments, 1.5 hours for the mid-point survey, approximately 2 hours for the 7 week/post-intervention surveys, as well as approximately 1 hour for the 1 month follow-up surveys. See Table 2 for the measurement schedule:

Table 2: Measurement Schedule for Phase 3

MEASURE	BASELINE	MIDPOINT	INTERVENTION END /7 WEEKS	1-MONTH FOLLOW- UP
Demographics	X			
MEAQ	x		x	x
CPVI	x	x	x	x
PHQ-9	x	x	x	x
VR-36	x	x	x	x
POQ-SF	x	x	x	x
SCID-5	x			
BPI	x			
CPAQ	x	x	x	x
Usability survey*			x	
SUS*			x	
WAIS-S*			x	
CSQ-8*			x	
Qualitative Interview			x	

*will only be assessed in invention group

Demographics, functional health, and pain measures.

Demographic measures will include age, gender, race and ethnicity, and education. We will also include questions related to medications currently being used for the management of physical or psychological conditions, self-reported using a single-item listing diagnoses, and at baseline and 7 weeks conduct a CPRS record review for such information. These measures will take approximately 10 minutes.

Feasibility and

Acceptability Measures: Feasibility outcomes will include recorded information on recruitment rates, retention rates within each condition, measure completion rates, how often Veterans access the website, and any reported problems with the website. This information will be collected by the research team.

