Pain-related Measures. At the beginning of each module, the Veteran will be asked to rate their current level of pain using a 11-item pain intensity scale. In addition, the following two assessments will be provided pre- and post- intervention: *Pain Outcomes Questionnaire – Short Form (POO-SF)*⁴⁷ is a 20-item inventory that assesses patient's ability to engage in functional activities related to daily living that may be impacted by pain interference; and *The Chronic Pain Acceptance Questionnaire (CPAQ)*⁴⁸ is 20-item survey measuring recognition of pain as not negating the ability to live valued life. We will also assess pain interference, again using the *Brief Pain Inventory*. This battery of pain -related measures will take approximately 25 minutes.

Mental Health Co-Morbidity Measures. To assess for important psychological co-morbidities in chronic pain treatment, we will administer the 9 – item Patient Health Questionnaire-9 (PHQ-9)⁶¹ to assess for depressive symptoms, and 20-item PTSD Checklist-5 (PCL-5).⁴¹ These surveys will take approximately 7 minutes.

Valued Living. *The Chronic Pain Values Inventory (CPVI)* is a 12-item self-report measure of the extent to which the patient is living in accordance with their values in areas such as work, health, and family, which is related to lower perceived disability and pain-related anxiety, as well as greater reported patient functioning even in the context of high levels of pain.⁶² This survey will take approximately 3 minutes.

Behavioral Avoidance. The *Multidimensional Experiential Avoidance Questionnaire (MEAQ)* is a 62-item self-report measure of experiential avoidance, including subscales on Behavioral Avoidance, Distress Aversion, Procrastination, Distraction & Suppression, Repression & Denial, and Distress Endurance.⁵⁰ This survey will take approximately 12 minutes.

Patient Satisfaction with Treatment: *Client Satisfaction Questionnaire-8. (CSQ-8)*⁵¹ This 8-item scale measures global satisfaction, perceived quality, and effectiveness of the proposed mental health treatment. This scale has been used in mental health and other health centers, and has acceptable internal consistency ($\alpha=.83-.93$). This survey will take approximately 2 minutes.

Therapeutic Alliance: *Working Alliance Inventory-Short Form (WAI-S)*⁵² This 11-item scale will be administered to obtain both an early and a late alliance assessment between the Veterans and VACT-

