Hypothesis One: We will observe increases in the means scores on pain acceptance, functioning, behavioral avoidance, mental-health symptoms (PTSD and depression), and values-oriented living given past ACT-based chronic pain interventions research for VACT-CP participants.

Hypothesis Two: We predict that there will be small- to no-change in means on pain levels, given research suggesting that behavioral intentions do not change pain levels overall.⁵⁸

To address Aim 3b, we will describe the outcome variable scores from pre- to post-intervention using subjective pain-related outcomes and quality of life measures. Because we have proposed a rolling design where changes in the delivery of VACT-CP intervention can be made with each wave of participants, the number of participants given the same version of the self-management program may be too few to test these outcome effects at a conventional level of significance. We will thus describe differences by reporting means and standard deviations pre- and post-levels of outcomes (pain acceptance, pain levels, pain functioning, behavioral avoidance, mental-health comorbidities, and values-oriented living). We will also use mental health measures to describe our sample and explore if groups are equivalent based on these measures.

Based on the intent-to-treat principle, all subjects enrolled in the pilot study treatment will be included in analyses, and the PI will conduct preliminarily analyses and descriptively report on the pilot RCT outcomes of the VACT-CP intervention in order to inform further refinements to VACT-CP. Additional outcomes of interest, including working alliance and treatment satisfaction will also be reported and described in terms of their means and standard deviations. Due to imprecise estimations due to small sample size, we will not report estimates of effect sizes as a specific hypothesis or aim; however, we will explore and report on descriptives (means, standard deviations) between pre- and post-scores.

Secondary Analyses, Aim 3c.

To evaluate the feasibility of recruiting the necessary sample for a larger randomized controlled trial by determining the effect size for future studies. Leon and colleagues⁵⁹ point out that a pilot study does not necessarily provide the meaningful effect size estimates necessary for planning subsequent larger studies due to the imprecision inherent in data from small samples. However, it will provide feasibility and acceptability data.

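### PTSD symptoms are a pre/post outcome in Aim 3b, but the Phase 3 measurement schedule has no PCL-5 row

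*Combined protocol and SAP*

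**What the plan says.** Three parts of the protocol bear on this.

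- **Analysis (3.5, Secondary Analyses, Aim 3b).** Hypothesis One states: "We will observe increases in the means scores on pain acceptance, functioning, behavioral avoidance, mental-health symptoms (PTSD and depression), and values-oriented living". The method is descriptive: "We will thus describe differences by reporting means and standard deviations pre- and post-levels of outcomes", and mental-health comorbidities are in the list of outcomes that follows. The same paragraph adds: "We will also use mental health measures to describe our sample and explore if groups are equivalent based on these measures".
- **Measures (3.4, Phase 3, Mental Health Co-Morbidity Measures).** The PHQ-9 is to be given for depressive symptoms, together with the "20-item PTSD Checklist-5 (PCL-5"). On the time for the two, the text says: "These surveys will take approximately 7 minutes". No visits are named.
- **Schedule (3.4, "Table 2: Measurement Schedule for Phase 3").** The table has four visit columns: baseline, midpoint, 7 weeks and one-month follow-up. The PHQ-9 is marked at all four. The PCL-5 does not appear. Section 3.3 gives this table its authority: "Veterans in both conditions will complete the assessment battery (see Table 2 for specific schedule").

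The only place where the PCL-5 is tied to a time point is Phase 2, among the measures taken at the start of the usability session: "Well-being measures will include psychological depression, Patient Health Questionnaire-9 (PHQ-9), and PTSD Check List (PCL-5").

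**The concern.** A pre/post summary needs a score at each end. The analysis section relies on PTSD scores and the measures section promises the instrument, but the table that staff would use to build visit packets and online surveys leaves it out. If that table is taken as complete, the PTSD part of Hypothesis One cannot be reported in either arm, and the check on whether the groups are equivalent has a depression score but no PTSD symptom score. If practice varies between the text and the table, the PCL-5 will be present for some of the 40 randomized Veterans and absent for others. A baseline score missed in either way cannot be collected afterwards.

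**Working it through.** No figure in the plan needs reproducing. The check sets the hypothesis, the measures text and the schedule side by side.

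**Step 1. Each Hypothesis One outcome against Table 2.**

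| Outcome | Instrument | Baseline | 7 weeks |
|---|---|---|---|
| Pain acceptance | CPAQ | yes | yes |
| Functioning | POQ-SF | yes | yes |
| Behavioral avoidance | MEAQ | yes | yes |
| Depression | PHQ-9 | yes | yes |
| Values-oriented living | CPVI | yes | yes |
| PTSD | PCL-5 | no row | no row |

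Scheduled before and after: 5 of 6. The hypothesis does not name instruments, so this matching is mine. Using the VR-36 instead of the POQ-SF for functioning leaves the count unchanged, because the VR-36 is also marked at both visits.

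**Step 2. Row count.** Table 2 lists Demographics, MEAQ, CPVI, PHQ-9, VR-36, POQ-SF, SCID-5, BPI, CPAQ, Usability survey, SUS, WAIS-S, CSQ-8 and Qualitative Interview. That is 14 rows, none of them the PCL-5. The table reads as intact, with all four columns and its footnote, and shows no sign of a lost or blacked-out row.

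**Step 3. Could another Phase 3 measure supply the score?**

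- The SCID-5 is given at baseline only, and section 3.4 limits its purpose to psychosis, substance use disorders and suicidality.
- The self-report diagnosis item and the chart review at baseline and 7 weeks could at most show that a PTSD diagnosis exists. They give no symptom mean or standard deviation.
- The Phase 2 PCL-5 belongs to a separate usability sample.

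**Step 4. Could the text set the visits without the table?** Section 3.3 says the full set of primary outcomes and process measures is repeated at 3 and 7 weeks, but it names no instruments. Table 2 is not uniform across visits: the MEAQ is not taken at midpoint and the BPI is taken only at baseline. A PCL-5 schedule therefore cannot be read off a general statement about the battery.

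**Step 5. Is Table 2 complete?** No. Section 4.6.1 requires the Columbia Suicide Severity Rating Scale at each assessment session, and it has no row either. The difference is that the text gives the Columbia scale its timing, whereas no Phase 3 passage names visits for the PCL-5.

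**Two smaller points, which carry no weight in the conclusion.**

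- Hypothesis One predicts a rise in every listed score. For PTSD and depression symptoms a rise is a worsening. For avoidance the same follows by inference, since the scoring direction of the MEAQ is not stated.
- Section 1.0, Phase 3 Objective 2, compares pain level with the wait-list. The only rating described as pain level is taken at the start of each module, which wait-list participants do not use before their follow-up. The VR-36, which includes bodily pain, is collected in both arms but is not designated for this comparison.

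**The case against.** The strongest reply is that this is a clerical omission. Section 3.4 states affirmatively that the PCL-5 will be given and pairs it with the PHQ-9 as a co-morbidity measure. Aim 3b promises levels of mental-health comorbidities before and after the intervention, so collection at baseline and at the end can be inferred. Table 2 is demonstrably incomplete: besides the Columbia scale, it does not show the chart review at 7 weeks, and it marks the alliance scale once although the text wants an early and a late assessment. The trial has one site, with the PI directing data management, so divergent practice between staff is speculative.

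The stakes are also modest. Aim 3b is secondary and descriptive, PTSD is not among the outcomes that section 1.0 lists for comparison with the wait-list, and the sample size for the later trial does not depend on it.

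Much of this stands. The missing row does not show that the PCL-5 will be skipped, patchy collection is a risk and not a prediction, and no test or pilot decision turns on the score. It does not remove the contradiction. An inference from the analysis section is not a schedule, and the document that section 3.3 names as the schedule says otherwise.

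**Conclusion.** The concern holds. The analysis plan and the measures text require a PTSD symptom score in Phase 3, and the cited schedule does not contain one. PTSD is the only one of six Hypothesis One outcomes without an instrument in Table 2 at baseline and 7 weeks. On the table as printed it is collected at 0 of 4 visits, against 4 of 4 for the PHQ-9.

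The loss of the PTSD summary and of the PTSD part of the equivalence check is conditional on staff following Table 2. Because the aim is secondary and descriptive, the consequence is confined to what this pilot can report. It should still be corrected, since a missed baseline cannot be made good.

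**What to change.** Choose one of two changes:

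1. Add a PCL-5 row to Table 2, marked at baseline and 7 weeks for both arms. These two visits are the minimum that Aim 3b needs; whether to match the four visits of the PHQ-9 is for the sponsor to decide.
2. Delete PTSD from Aim 3b and the PCL-5 from the Phase 3 measures.

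The first costs one table row. Section 3.4 already counts about 7 minutes for the PHQ-9 and PCL-5 together, so it adds no time beyond what the text plans.

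Two wording changes can be made at the same time, with no new data collection:

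- Reword Hypothesis One to predict higher mean pain acceptance, functioning and values-oriented living, and lower mean behavioral avoidance and PTSD and depression symptoms, in VACT-CP participants.
- Designate for pain level one measure already collected in both arms at baseline and 7 weeks, for example VR-36 bodily pain, stating that it will be scored separately. Describe the module ratings for the VACT-CP arm only.

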4.0 Human Subjects

4.1 General Characteristics

Phase One: We will aim to recruit a maximum of 12 clinical care providers at the VA Bedford Healthcare System who work with Veterans with chronic pain, over the course of 3 to 6 months. [name] or another member of the study team will send emails to providers who have been identified as working with patients with chronic pain to invite them to join the study, as identified by study staff. The general features of this participant sample will be clinical-care providers (nurses, doctors, psychologists, psychiatrists) over the age of 18 who work at the Bedford VAMC and currently provide pain-management care treatment to Veterans. In order to ensure a representative mix of clinical-care pain providers at the VA Bedford, we will aim to ideally recruit 2-3 psychologists, 2-3 nurses, 2-3 MDs, and 2-3 psychiatrists total, and may engage in more targeted recruitment in order to meet the **minimum goal of two providers in each area**. Interviewing and incorporating provider feedback is important at this development stage, so that chronic-pain clinical providers have their perspectives included into the creation of this VA platform. As content experts and future clinicians who would likely refer Veterans to this program, they should be able to provide input related to improving the system and adding potential important treatment options to the site. This project will allow for feedback and preliminary usability information to revise the developing chronic-pain treatment platform.

Providers and staff at various VA Bedford clinical sites will be identified using a reputation-based snowball design, wherein persons who are recruited will be asked to pass along recruitment information (flyers, initial email) to other chronic pain providers they believe might be interested in this study. We may make presentations to groups of providers who are likely to care for patients with chronic pain issues at their team meetings to tell them about the study. A small group of individuals interested in discussing online interventions for pain will initially be identified with the help of local providers, researchers and administrators, and only research staff will recruit these persons via an IRB-approved email and potentially a corresponding phone call.

Interested individuals will be briefly screened by phone for eligibility. No individually-identifiable data will be captured from the brief phone screening; data will be saved ONLY for purposes of tracking screening eligibility rates and reasons for ineligibility. This will inform our future referral strategy and resource planning for a future small pilot usability study on VACT-CP. The racial and ethnic characteristics of the sample are likely to reflect that of clinical-care providers at the VA Bedford. In addition, we may post flyers in approved locations around the facility and affiliated ambulatory services including community-based outpatient clinics (CBOCs) and share flyers with clinical staff who are most likely to have contact with other chronic-pain care providers who might be interested in the study.

Phase Two: We will aim to recruit a maximum of 15 Veterans recruited from the Bedford VA. Veterans at the Bedford VAMC will be identified as having a chronic, non-cancer pain diagnosis using CPRS chart review, hear about the study from providers, or are self-referred. Veterans from the community may contact us by learning about the study from posts in the community (e.g., craigslist). A 2019 review revealed that there were 2,605 Veterans who were seen over the past year (i.e., having had at least two appointments for pain) at the Bedford VA with chronic, non-cancer pain concerns, so we should have no difficulty recruiting the proposed number of participants.

Potential participants will be pre-screened by phone to determine whether basic study eligibility criteria are met. Individuals who remain eligible after the phone pre-screen will be scheduled for the research session. At the beginning of the research session, we will provide participants with detailed information about the study and obtain verbal informed consent. Following informed consent, participants will complete study assessments and engage in a usability testing. Participants will have a \$40 gift card mailed to their home following the research session.

Phase Three: We will aim to recruit up to 60 participants over fifteen months total to allow for the desired final 40 participants screened as eligible and randomized into the pilot RCT study, specifically aiming for recruiting 3-4 participants per month. Subjects for the proposed study will be recruited over the course of approximately 15 months and be screened according to their presence of chronic pain and other inclusion/exclusion criteria. First, potential participants will be pre-screened by phone to determine whether basic study eligibility criteria are met. Individuals who remain eligible after the phone pre-screen will be randomized in a 1:1 ratio. Veterans randomized to VACT-CP will receive 7 online-module based weekly sessions of treatment via personal computer or provided laptop with wireless accessibility at the Bedford VAMC. Veterans in the waitlist control will be provided with a list of common pain resources at the Bedford VAMC. Subjects will be paid \$60 for the baseline assessment, \$40 at the midpoint testing visit/week 3 for waitlist control, and, \$60 for the end of treatment (Session 7)/end of week 7 for control group participants and \$40 for a one-month follow-up (total; \$200 total).

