During each wave of testing, Veterans will interact with the VACT-CP online treatment to: 1) gather feedback regarding acceptability and usefulness of the treatment, 2) gather and analyze complementary data from SUS-8, 3) address any technological issues as they arise, and 4) examine preliminary data from this phase of the study. Modifications to the website will be based upon: 1) acceptability and feasibility of the online treatment, and 2) qualitative feedback obtained from patients, therapist, and mentors. Individual feedback sessions at the end of Phase 2 will be held to gather information for refining the treatment intervention and make it acceptable to patients.

We anticipate that our Veteran intervention reviewers might miss bugs or other user interface problems and anticipate that some revisions to the online system and program may need to be made. For instance, one potential issue that may arise might be an inability for the Veteran to read the text on the screen. After receiving this information during an initial feedback round, the researchers will amend the program with a potential solution, i.e., text size or text color being altered, with the revised version then being piloted in the next round of Veteran user testing. Some usability challenges will be addressed with introductory handouts/tutorial materials/orientation to the program at the beginning of the intervention session. In addition, large organizational issues will be discussed before moving on to platform refinement.

Phase 3: Data Collection

Callers will be initially screened by phone. Eligible participants will be scheduled for an in-person assessment or phone-conference with research staff. At this assessment, research staff will confirm study eligibility and obtain informed consent and administer the Structured Clinical Interview for DSM-5

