4.4 Inclusion/Exclusion Criteria

Phase One:

Inclusion Criteria

- 1) Currently working at the VA Bedford Healthcare System or one of its affiliated CBOCs in a clinical capacity, including mental health, physicians, nursing, pharmacists, or primary care/behavioral health staff
- 2) Currently seeing Veterans to assist in their management of chronic pain

Exclusion Criteria.

- 1) Any cognitive or physical impairment that would interfere with study participation of using a computer and providing verbal feedback.

Phase Two:

Inclusion Criteria

- 1) Current diagnosis of non-cancer chronic pain
- 2) Competent to provide written informed consent
- 3) Ages 18 and older
- 4) Access to the internet at least weekly through a computer

Exclusion Criteria

- 1) Any cognitive or physical impairment (e.g., auditory or sight issues issues) that would interfere with study participation of using a tablet/computer and providing feedback.

Phase Three:

Inclusion Criteria

- 1) Current diagnosis of non-cancer chronic pain, defined as 1) at least one pain-related diagnosis indicated by an ICD-9 or -10 code related to either Musculoskeletal pain or Joint Problems/Osteoarthritis or 2) presence of chronic pain of at least mild to moderate severity as indicated by two or more NRS pain scores of ≥ 4 at three separate VA outpatient visits in past year based on a CPRS record review;
- 2) Has a working, high-speed wireless internet connection at home, or is willing to access sessions either at the Bedford VAMC by using a provided laptop in a secure space
- 3) Competent to provide written informed consent
- 4) Ages 18 and older.

Exclusion Criteria

- 1) Any current or lifetime DSM-5 psychotic disorder
- 2) Current or recent (within 1 month of study entry) DSM-5 alcohol or drug use disorder
- 3) Current use of any other chronic pain-related behavioral or psychological treatment
- 4) Any cognitive impairment that would interfere with study participation
- 5) Clinically significant suicidality within the past year
- 6) Presence of any clinical features requiring a higher level of care (inpatient or partial hospital treatment)
- 7) Any cognitive or physical impairment that would interfere with study participation of using a laptop/computer and providing feedback]

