Phase Two: All potential participants will be screened by phone. Potential participants will be identified via self-referral, information is provided by clinical providers or VA staff. Veterans may be provided information on the study by providers and those Veterans tell providers they would like to be contacted by study staff. In addition, Veterans may be identified via a medical record search of potential candidates with a non-cancer chronic pain disorder that come to the clinics listed above. If potential research participants call us about their interest in participating in the study, we will use the attached screening tool and script to assess their eligibility for the study. Patients who are initially screened via

prescreening through the VA Medical Records System, CPRS will be sent a letter regarding their interest, and then called after two weeks if they do not opt out. We will call Veterans to determine their interest in the study, and conduct a screening with the attached screening tool and script. For participants that have indicated to their providers that they would like to be called about the study, and providers have passed on this information to research staff, then research staff will contact them for an initial prescreen for the study (see attached phone script and screen).

Potential subjects will initially be pre-screened by phone to determine whether basic eligibility criteria are met for the study (e.g., age, diagnosis, computer Internet access). Phone pre-screens will be scripted and completed by trained interviewers. Individuals who remain eligible to participate after completion of the phone pre-screen will be invited to participate in usability testing.

Phase 3: We will utilize the same screening procedures as Phase 2 (phone screen for Phase 3 will be different. See attached document).

4.5.1a HIPAA Authorization for Recruitment and/or Screening:

Phase One: We will only ask potential participants if they currently work at the Bedford VAMC, and if they treat Veteran patients for chronic pain concerns. Participants will not be asked for any information regarding their person health or health care.

Phase Two and Phase Three: A request to use identifiable information in the conduct of this research study under a waiver of authorization for recruitment and screening was submitted with this protocol. The identifiable information being requested is:

To use during the recruitment process:

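### Two Phase 3 passages, read literally, randomize before eligibility is confirmed, and no section says the baseline battery is completed before allocation

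*Combined protocol and SAP*

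**What the plan says.** All references are to Phase 3 in the combined protocol and SAP.

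- **Section 4.1.** After a phone pre-screen of basic criteria: "Individuals who remain eligible after the phone pre-screen will be randomized in a 1:1 ratio". The same paragraph also describes the target of 40 as people found eligible by screening and then randomized.
- **Section 3.4.** After the phone screen, "Eligible participants will be scheduled for an in-person assessment or phone-conference with research staff". Then: "At this assessment, research staff will confirm study eligibility and obtain informed consent and administer the Structured Clinical Interview for DSM-5", given "to assess for potential psychosis, substance use disorders, or clinically-significant suicidality". Next: "Eligible subjects will then complete self-report measures". Randomization is not mentioned.
- **Section 4.4.** Seven exclusions are listed. Three match the SCID-5 content: "Any current or lifetime DSM-5 psychotic disorder", "Current or recent (within 1 month of study entry) DSM-5 alcohol or drug use disorder", and clinically significant suicidality in the past year.
- **Section 4.5.1b.** Interested Veterans are screened by phone and those eligible are booked for a session. Those enrolled remotely then give verbal consent and are randomized from a schedule made beforehand. No eligibility step is named between consent and randomization.
- **Section 4.5.2.** At most 60 are consented, 2 of every 3 are assumed eligible, and a subject is enrolled after consent if the criteria are met.
- **Section 1.0.** At most 40 are enrolled and randomized.
- **Section 3.3.** Screening is done before enrollment, and randomization is described next. The baseline battery is mentioned later, for both conditions.
- **Section 3.5, Aim 3b.** The intent-to-treat set is worded as those enrolled in the pilot treatment.

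**The concern.** Sections 4.1 and 3.4 name a different next step for the same people, those still eligible after the phone screen. One randomizes them. The other books an assessment at which eligibility has yet to be confirmed. Section 4.5.1b adds a further version for remote participants. Staff working from 4.1 or 4.5.1b alone could allocate a Veteran before the SCID-5 has been given.

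The study is unblinded (section 4.6.2.2) and the control is a waitlist (section 3.2). Two things are then at stake. Veterans could be removed as ineligible after allocation, by staff who know the arm. Baseline self-reports could also be completed by Veterans who already know whether they will get the program or wait.

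The results exposed are retention in each condition, the check that the groups are equivalent at baseline, and the pre/post means and SDs (section 3.5, Aims 3b and 3c). Retention matters beyond this pilot, because Aim 3c proposes to build it into the sample size of the next trial.

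**Working it through.** **1. The plan's own flow.** Inputs: at most 60 consented and 2 in 3 eligible (section 4.5.2); at most 40 randomized (section 1.0).

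- Eligible = 60 × 2/3 = 40, which equals the maximum randomized.
- In reverse, 40 ÷ (2/3) = 60.

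The figures reproduce exactly, but only if eligibility is settled after consent and before randomization.

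**2. The literal order, kept within the cap.** Suppose 40 are randomized before eligibility is confirmed, and the 2-in-3 yield applies to them.

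- Eligible among the 40: 40 × 2/3 = 26.7, about 27, or about 13 per arm.
- Ineligible after allocation: 40 − 26.7 = 13.3, about 13.
- If eligibility is confirmed first, the number is 0.

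The yield is a planning assumption stated for consented people. Applying it to people randomized straight after the phone pre-screen is a further assumption.

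**3. What this could do to retention (illustration).** Section 3.3 assumes 30% attrition after randomization.

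- Eligibility first: 40 × 0.70 = 28 retained, and 28/40 = 70%.
- Literal order: 26.7 × 0.70 = 18.7 retained. With ineligible Veterans counted as losses, 18.7/40 = 47%. With them left out, 18.7/26.7 = 70%.

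The plan does not say which count would be used.

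**4. Baseline against allocation.** No arithmetic applies here, so the passages are compared.

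- Section 3.4 puts the self-reports after eligibility is confirmed. That can be read as the same visit, before allocation, but the section does not mention allocation.
- Section 3.3 mentions the battery after randomization. It also mentions it after the weekly sessions, so its order is not chronological and settles nothing.
- Table 2 and section 4.5.2b name a baseline time point without ordering it against randomization.

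The number of baselines given with the arm known is therefore 0 if baseline precedes allocation and up to 40 if it follows. The documents do not fix it.

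**The case against.** The best defense is that this is incomplete wording. The paragraph in 4.1 is a recruitment summary. It also leaves out consent, which 4.5.1b and 4.5.2b plainly place before randomization, and the SCID-5 step can be supplied from 3.4 in the same way. Section 3.4 never mentions randomization, so it cannot state a contrary point for it. Section 4.5.1b may be shorthand too: its Phase Two counterpart skips baseline measures that 3.4 requires. The Phase 3 phone form differs from the Phase 2 form (section 4.5.1) and is not in the documents, so it may screen more fully. Section 4.6.1 already has suicide risk assessed at the initial phone screen.

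Most of this stands, and it limits how likely and how large any harm is. It does not make the sections agree. In 4.1, the matching Phase Two sentence leads to a session, then consent, then assessments; the Phase Three sentence leads to randomization. Knowing what was probably meant is a reason to write it down.

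A reader might also infer more than the documents support:

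- **That the design deliberately randomizes before eligibility.** Sections 1.0, 3.3, 4.1 and 4.5.2 point the other way.
- **That 60 would be randomized and 20 prove ineligible.** The cap of 40 in section 1.0 rules this out.
- **That one third is an upper limit on ineligibility.** It is an expected rate.
- **That 3.3 schedules baseline after allocation.** It only mentions it later in the text.
- **That low precision of the equivalence check shows bias.** With 20 per arm, the 95% half-width for a baseline difference is 2.024 × √(2/20) = 0.64 SD. That measures imprecision and says nothing about the size of any bias from knowing the arm.

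**Conclusion.** The point holds as a sequencing inconsistency plus an omission. Read literally, 4.1 and 4.5.1b are out of line with the rest of the plan, whose text and figures fit eligibility first. Separately, nothing states that baseline comes before allocation.

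The size is conditional. It rests on staff following 4.1 or 4.5.1b literally, on the cap of 40 being kept, and on the 2-in-3 yield carrying over. Under those assumptions about 13 of 40 would be expected to be found ineligible after allocation. The figure for baselines, up to 40 with the arm known, requires only that baseline follow allocation. If eligibility and baseline are completed first, both numbers are 0.

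No between-arm efficacy test is planned, and Aim 3a concerns usability and use, so the consequence stays within the descriptive and feasibility results. Severity is minor to moderate.

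The intent-to-treat wording is a smaller, separate matter. Sections 1.0 and 3.3 pair enrollment with randomization, so enrolled in Aim 3b plausibly means randomized. Even so, the plan has no rule for someone found ineligible after allocation.

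**What to change.** Reconcile sections 3.3, 3.4, 4.1, 4.5.1b and 4.5.2 to one Phase 3 sequence that applies to in-person and remote participants alike:

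1. phone pre-screen;
2. consent;
3. SCID-5 given and eligibility confirmed;
4. baseline battery completed;
5. assignment released.

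In 4.5.2, remove the Phase 2 usability-session wording from the Phase Three eligibility sentence.

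As a minor wording change in section 3.5, Aim 3b, state that the intent-to-treat set is all randomized participants. Report anyone found ineligible after allocation by arm, separately from attrition.

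The cost is protocol wording and the order of steps already planned. No new visits, staff or participants are needed, and the flow of 60 consented to 40 randomized is unchanged.
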